
 1. Thrombin generation assay (TGA) parameters (lag time, time to peak thrombin generation, peak thrombin generation, and endogenous thrombin potential [ETP]) 2. Bleed and pain severity scores as measured by the Haemo-SYM questionnaire 3. HRQoL as assessed using EQ-5D and mental domain and component scores of the SF-36 4. Healthcare resource utilization 	
INVESTIGATIONAL PRODUCT(S), DOSE AND MODE OF ADMINISTRATION	
Active Product	
BAX 855 Dosage form: injection, powder, lyophilized, for solution
 
Dose and Dosage frequency: BAX 855 dose will be PK-guided to maintain FVIII target trough levels of 1-3% or approximately 10% (8-12%) at the following dosing frequencies: FVIII trough levels of 1-3%: approximately twice weeklyⁱⁱ FVIII trough levels of approximately 10% (8-12%): every other dayⁱⁱⁱ
 
Mode of Administration: intravenous bolus

SUBJECT SELECTION	
Targeted Accrual	Approximately 116 subjects will be enrolled to have 96 subjects evaluable (48 in each prophylaxis dosing arm).
Number of Groups/ Arms/Cohorts	2

Inclusion Criteria for Subjects Transitioning from Another BAX 855 study:
 
 1. Subject has completed the end of study visit of a BAX 855 study or is transitioning from the ongoing Continuation Study 261302 2. Subject is either receiving on-demand or prophylactic treatment with BAX 855 and had an ABR of ≥ 2 documented and treated during the past 12 months 3. Subject is human immunodeficiency virus negative (HIV-); or HIV+ with stable disease and CD4+ count ≥ 200 cells/mm³, as confirmed by central laboratory 4. Subject is willing and able to comply with the requirements of the protocol 
Inclusion Criteria for Newly Recruited Subjects:
 
 1. Subject is 12 to 65 years old at the time of screening 2. Subject has severe hemophilia A (FVIII clotting activity <1%) as confirmed by central laboratory OR by historically documented FVIII clotting activity performed by a certified clinical laboratory, optionally supported by a FVIII gene mutation consistent with severe hemophilia A 3. Subject has been previously treated with plasma-derived FVIII concentrates or recombinant FVIII for ≥ 150 documented EDs 	

ⁱⁱ Twice weekly: infusion on day 3 or 4, at 2 different doses to cover the different treatment intervals, or every 3.5 days. According to individual PK, frequency may be adjusted based on FVIII trough levels.

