6.3 Population to be Studied

Adolescent and adult subjects (aged 12-65 years) with severe hemophilia A (FVIII <1%), of all races and ethnic groups, without history of or currently confirmed FVIII inhibitors (≥ 0.6 Bethesda Units [BU]) will be studied. All subjects will have been previously treated with pdFVIII or rFVIII concentrates with ≥ 150 documented exposure days (EDs) (previously treated patients; PTP). Subjects receiving prophylaxis and on-demand treatment will be included in this study and they must have had at least 2 documented and treated bleeds within the 12 months prior to enrolment.

Justification for enrollment of adolescent subjects is based on the nonclinical safety requirements outlined in the ICH M3 Guideline, Section 12 as well as the ICH E11 Guideline on clinical investigation of medicinal products in the pediatric population. Hemophilia is a serious and potentially life-threatening disease. Adolescent subjects, in particular if they are physically active, are expected to benefit from a new treatment approach with target FVIII trough levels of approximately 10% using a new recombinant full-length rFVIII molecule with an extended half-life. Moreover, results from nonclinical repeated toxicology studies, the core safety pharmacology package and the completed clinical Phase 1, Phase 2/3 pivotal, Phase 3 pediatric studies, as well as the ongoing Phase 3 continuation and surgery studies have not raised any safety or tolerability concerns. Furthermore, the parent protein molecule ADVATE has been used extensively in the entire pediatric population with no unforeseen adverse events (AEs).

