- Study 261204 is a Phase 3 study to assess efficacy in subjects undergoing major or minor elective or minor emergency surgical, dental, or other invasive procedures. The dose and frequency of BAX 855 administered is individualized based on the subject's PK parameters (determined from a presurgical assessment) for major surgeries and IR for minor surgeries and the FVIII target levels required for the planned procedure. Based on an interim analysis, perioperative and intraoperative hemostatic efficacy of BAX 855 was rated as "excellent", for 15/15 procedures. The postoperative efficacy of BAX 855 was rated as "excellent" for 13 procedures, "good" for one procedure, and the rating was pending for one procedure at the time of data cut-off. These results of 11 major and 4 minor surgeries in 15 hemophilia A subjects indicate that BAX 855 has excellent efficacy for perioperative use in major surgery with blood loss comparable to that expected for the same type of procedure performed in a non-hemophilic subject.
- Study 261302 is a Phase 3b continuation study evaluating safety and efficacy in the prophylaxis of bleeding in subjects who have completed previous BAX 855 studies. This study also explores different treatment regimens. After closure of enrollment for pediatric study 261202 and pivotal study 261201, the continuation study is open also to BAX 855 naïve pediatric subjects.
- Study 261203 is a Phase 3, prospective, open-label, multicenter study to assess the safety, immunogenicity and hemostatic efficacy of BAX 855 in previously untreated patients <6 years of age with severe hemophilia A (baseline FVIII level <1%) and <3 EDs to ADVATE, BAX 855, or fresh frozen plasma in at least 100 evaluable subjects. The subject's participation will last approximately 2 years, depending on the type of treatment, and up to 5.5 years in total, in case of inhibitors.

The results to date demonstrate that BAX 855 is safe and efficacious in treating bleeding episodes and in prophylaxis, including long-term prophylaxis, administered twice weekly in children, adults, and adolescents with severe hemophilia A as well as in surgical prophylaxis. In addition, the data consistently demonstrate prolonged circulation of BAX 855 in comparison with the parent molecule ADVATE.

Additional information from clinical studies can be found in the BAX 855 IB.

6.5 Evaluation of Anticipated Risks and Benefits of the Investigational Product to Human Subjects

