8.2 Overall Study Design

This study is a Phase 3, prospective, randomized, open-label, multicenter study to compare the safety and efficacy of PK and FVIII trough level-guided BAX 855 treatment targeting FVIII trough levels of 1-3% or approximately 10% (8-12%) in a total of 96 evaluable (48 in each of 2 study arms) adolescent and adult PTPs with severe hemophilia A (<1% FVIII). Approximately 116 subjects will be enrolled for a total of 96 evaluable subjects (assuming a dropout rate of close to 10% and 10-15% of subjects being non-compliant). Subjects from the BAX 855 continuation (261302) the BAX 855 surgery (261204) study, the BAX 855 pediatric (261202) study^v, and newly recruited subjects including BAX 855-naïve subjects will participate.

Subjects will be screened per protocol inclusion/exclusion criteria and, following confirmation of eligibility, will undergo an initial PK assessment following a single administration of BAX 855 (60 ±5 IU/kg) to determine PK parameters. Following the PK assessment, subjects will be randomized to one of 2 dosing regimens: the standard treatment arm will target FVIII trough levels of 1-3% and the second, intensified treatment arm will target trough levels of approximately 10% (8-12%) FVIII. The dose and frequency will be based on each subject's individual PK. More frequent dosing should be considered if single doses of >80 IU/kg are required or regular FVIII peak levels of 200% would be reached.

^v In case subject is at least 12 years of age at the time of informed consent of this study.

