9. SUBJECT SELECTION, WITHDRAWAL, AND DISCONTINUATION

9.1 Inclusion Criteria

9.1.1 Subjects Transitioning from another BAX 855 Study

Subjects transitioning from another BAX 855 study who meet **ALL** of the following criteria are eligible for this study:

1. Subject has completed the end of study visit of a BAX 855 study or is transitioning from the ongoing Baxalta Continuation Study 261302
2. Subject is either receiving on-demand treatment or prophylactic treatment with BAX 855 and had an ABR of ≥ 2 documented and treated during the past 12 months
3. Subject is human immunodeficiency virus negative (HIV-); or HIV+ with stable disease and CD4+ count ≥ 200 cells/mm³, as confirmed by central laboratory
4. Subject is willing and able to comply with the requirements of the protocol

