21.2 Detailed Flow Diagram of Study Procedures

Before **any** study procedures are performed, informed consent must be obtained from each subject.

Screening Visit

The screening procedures differ according to whether the subject is **transitioning from a previous BAX 855 study** (see Section A) or is newly recruited (see Section B). If the sponsor decides a transitioning subject requires a PK Assessment, then from the screening visit onwards procedures are identical to those for newly recruited subjects. If no PK Assessment is required, the next visit for transitioning subjects is the Baseline Visit once randomization is performed.

Evaluations must be completed within 56 days of the screening visit.

No washout is required but whenever possible the screening visit should be scheduled shortly before the next scheduled prophylactic infusion when baseline FVIII trough levels are reached in case the subject receives prophylactic treatment.

A: Subjects transitioning from other BAX 855 studies

The screening visit coincides with the end of study visit of the previous BAX 855 study; the subject must not be actively bleeding. If applicable, BAX 855 will be administered for IR determination based on the protocol of the previous study.

Informed consent must be obtained at enrollment at the latest (prior to any study-specific procedure); to give the subject sufficient time to review the ICF, this document should preferably be provided prior to the end of study visit of the previous study.

The relevant data obtained at the end of study visit of the previous BAX 855 study will be transcribed to the screening visit eCRF of this PK-guided dosing study, and where possible, duplication of blood draws or evaluations will be avoided.

The following procedures will be performed:

Clinical Assessments:

- Assessment of inclusion/exclusion criteria
- PROs (or can be done at Baseline visit) should be determined prior to any other study specific procedures:
 - Haemo-SYM questionnaire
 - EQ-5D
 - SF-36
 - Physical activity questionnaire
 - Health Resource Use

Laboratory Assessments:

Blood will be drawn for the following additional assessments:

- Screening tests:
 - CD4 count in subjects who are HIV positive
 - Viral serology (if any positive, test to be confirmed with a second sample) :
 - HIV: HIV-1 and HIV-2 Ab
 - HBV: HBsAg, HBsAb, HBcAb
 - HCV: HCVAb (PCR to be performed if positive)
- Pregnancy test, if applicable

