2. STUDY DESIGN

This study is a Phase 3, prospective, randomized, open-label, multicenter study to compare the safety and efficacy of a PK-guided BAX 855 treatment regimen targeting two different FVIII trough levels of 1-3% and approximately 10% (8-12%) in adolescent and adult, previously treated patients (PTPs) with severe haemophilia A (<1% FVIII) between the ages of 12 and 65 years inclusive. The study plans to include subjects from other BAX 855 studies as well as BAX 855-naïve subjects.

Enrolled subjects are to undergo an initial PK assessment following a single administration of BAX 855 to determine the subject's individual PK parameters to tailor the dose for the targeted FVIII trough levels.

The duration of subject participation in the study is approximately 15 to 16 months from enrollment to subject completion (i.e. last study visit), unless prematurely discontinued.

An optional repeat PK assessment at steady state should be performed after nine months of treatment administration.

The use of any FVIII concentrate other than BAX 855 during the course of the study, following the first BAX 855 PK-guided prophylactic infusion at baseline, is not permitted and will result in the immediate withdrawal of the subject.

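### The eligibility lists for transitioning subjects carry no age limit and no exposure-day requirement, so they can admit subjects whom protocol section 6.3 says are not studied

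*Protocol*

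**What the plan says.** Section 6.3 of the protocol defines the population as "Adolescent and adult subjects (aged 12-65 years) with severe hemophilia A" and adds that all subjects have at least 150 documented exposure days to FVIII. Sections 8.1 and 8.2 speak of adolescent and adult previously treated patients. SAP section 1 gives the same age range, and SAP section 2 describes subjects "between the ages of 12 and 65 years inclusive".

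Eligibility is set by two separate pairs of lists. For the transitioning route, section 9.1.1 opens with "Subjects transitioning from another BAX 855 study who meet" and states that those who satisfy all the listed "criteria are eligible for this study". It lists four items: the entry route ("Subject has completed the end of study visit of a BAX 855 study or is transitioning from the ongoing Continuation Study 261302", worded almost identically in the Synopsis), current BAX 855 treatment with at least 2 documented and treated bleeds in the past 12 months, HIV/CD4 status, and willingness to comply.

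Section 8.2 names three source studies: continuation study 261302, surgery study 261204 and pediatric study 261202. Footnote v, whose marker stands on 261202 only, reads: "In case subject is at least 12 years of age at the time of informed consent of this study". Section 6.4.2 says of 261302 that, after enrollment into 261201 and 261202 closed, "the continuation study is open also to BAX 855 naïve pediatric subjects".

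**The concern.** The criteria that a site applies to a transitioning subject are wider than the population the protocol says it studies. The new-subject list contains both the age range and the exposure-day minimum; the transitioning list contains neither. The age footnote covers the direct route from the pediatric study but not the indirect route through the continuation study.

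Three things are at stake. The randomized population may not match the one described. The justification in section 6.3 covers adolescents and does not extend to children under 12. The argument in section 6.5 that inhibitor risk is low rests on a high degree of previous FVIII exposure, which this route does not require. In the analysis, a subject under 12 could be randomized and treated, and so enter the Full and Safety Analysis Sets, without belonging to any SAP age group.

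**Working it through.** No sample-size, power or alpha figure is involved, so the check sets the texts side by side.

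| Element | Stated population (6.3) | New subjects (9.1.2, 9.2.2) | Transitioning subjects (9.1.1, 9.2.1) |
|---|---|---|---|
| Age | 12 to 65 | 12 to 65 at screening | none |
| Exposure days | at least 150, all subjects | at least 150 documented | none |
| Treated bleeds, past 12 months | at least 2 | at least 2 | at least 2 |
| Weight | not stated | excluded if <35 kg or >100 kg | excluded if <35 kg or >100 kg |

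Of the 4 transitioning inclusion items, 0 concern age or exposure days; of the 10 transitioning exclusion items, 0 do. The Synopsis gives the same lists, so this is not a slip in one copy.

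**Under 12.** Section 6.4.2 says that 261302 takes subjects who completed earlier BAX 855 studies and naïve pediatric subjects. Section 6.5 confirms that subjects who began in the pediatric study continued into it. Footnote v does not apply to 261302. A child in 261302 who weighs at least 35 kg, had at least 2 treated bleeds in 12 months and meets the remaining items satisfies 9.1.1 and 9.2.1.

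**Over 65.** No upper limit applies to any transitioning subject. Section 6.4.2 gives 18 to 65 as the entry range of 261101, and section 6.5 says that Phase 1 subjects continued into 261302, so someone near the limit at first entry could since have passed it. The documents identify no such subject.

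**Fewer than 150 exposure days.** No transitioning item refers to exposure days. The documents give no exposure-day entry requirement for the three source studies named in 8.2, so whether anyone enters this way cannot be settled from them.

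**Analysis.** SAP sections 4.2 and 4.3 define the Safety and Full Analysis Sets without reference to age. SAP section 5.12 defines age groups as 12 to <18 and 18 or over (EMA), and 12 to <17 and 17 or over (FDA). A subject with a derived age below 12 is in neither scheme. SAP section 6.2 derives age as year of reference start date minus year of birth. That difference equals the true age if the birthday has passed by the start date, and the true age plus 1 if it has not. So:
- true age 11, birthday passed: derived 11, no age group;
- true age 11, birthday still to come: derived 12, counted as an adolescent;
- true age 10 or younger: derived at most 11, no age group.

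A subject over 65 falls in the upper group of both schemes and is not lost.

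**Size of one subject.** 116/2 = 58 per arm; 1/58 = 0.017, or 1.7% of an arm.

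**The case against.** The strongest reply is that the intent is plain. Section 6.3 fixes 12 to 65 and 150 exposure days for all subjects, sections 8.1 and 8.2 say adolescent and adult, the SAP repeats the range, and nothing invites a child under 12. This stands as to intent: it is a drafting inconsistency, and the documents do not support reading it as a decision to enroll children. It does not remove the contradiction, because 9.1.1 says in terms that those who meet its list are eligible. SAP section 6.1 also names a separate eligibility eCRF panel for transitioning subjects. If that panel follows 9.1.1 and 9.2.1, an under-12 entrant would raise no exception.

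Four stronger readings are tempting and should not be drawn.

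- **That all 66 children treated in 261202 are candidates.** Footnote v bars direct entry from 261202 under age 12, the documents do not say how many of these children moved to 261302, and every other criterion still applies. In 261202, 37.9% of subjects had no bleeds and the median ABR was 2.00, so the rule of at least 2 treated bleeds would probably remove a good share before the 35 kg minimum removes more.
- **That an under-12 subject vanishes from every by-age table.** The calendar-year derivation places some 11-year-olds in the youngest group, so this is possible but not assured.
- **That the lack of a pregnancy criterion puts subjects outside the stated population.** Section 6.3 says nothing on pregnancy. Section 21.2 schedules "Pregnancy test, if applicable" at transitioning screening, section 10.6 names pregnancy as an example of a physician-decision reason for discontinuation, and section 13.2.4 requires reporting and follow-up.
- **That the lack of a hypersensitivity exclusion does so.** Section 6.3 is silent here too. Transitioning subjects must already be receiving BAX 855, section 6.5 reports no allergic or hypersensitivity adverse events in previously treated patients, 9.2.1 excludes clinically significant illness that in the investigator's opinion would affect safety, and 9.3 withdraws a subject after a severe anaphylactic reaction.

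The last two are secondary differences from the new-subject list, to be reconciled if unintended.

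**Conclusion.** The point holds for age and exposure days. The operative criteria for transitioning subjects can admit someone under 12, over 65, or with fewer than 150 exposure days, and each case contradicts section 6.3. The two age cases also contradict SAP sections 1 and 2, and the under-12 case contradicts sections 8.1 and 8.2.

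The effect is probably small. The documents do not give the number of transitioning candidates affected, and the weight and bleeding criteria would keep out many children. The primary test, the 48 evaluable subjects per arm and the stated power are unaffected. The analysis consequence is limited to an under-12 subject possibly having no age group.

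The conclusion assumes that sites and eCRF checks apply 9.1.1 and 9.2.1 as written. The entry criteria of the source studies are not fully visible, so the exposure-day and over-65 cases are gaps in the rule and not demonstrated entries.

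**What to change.** Reconcile the Synopsis and sections 9.1.1 and 9.2.1 with section 6.3 by applying the stated 12 to 65 age range and the requirement of at least 150 documented exposure days to all entrants. Extend footnote v to every source study. The new-subject list measures age at screening and footnote v at informed consent, so state one time point for both routes. Add matching checks to the transitioning eligibility eCRF panel. In the same edit, decide whether the missing pregnancy and hypersensitivity items were intended and say so.

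If enrollment has closed, verify age and exposure days for every transitioned subject, list anyone outside section 6.3, and state where a subject with a derived age below 12 appears in the by-age tables.

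The cost is a few lines of text and the eCRF checks. Two downsides are real but small. A few transitioning candidates may be lost. Exposure days will also need confirmation, because the data transcribed at transitioning screening (section 21.2) do not name cumulative exposure days and the medication history in section 21.3 covers only the last year of FVIII therapies.

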5. LIST OF ABBREVIATIONS

Abbreviation	Definition
ABR	annualized bleeding rate
AE	adverse event
AJBR	annualized joint bleeding rate
ALT	alanine aminotransferase (SGPT)
AST	aspartate aminotransferase (SGOT)
AUC	area under the curve
AUC(0-∞)	area under the plasma concentration curve from 0 to infinity
BAX 855	product code name for Baxalta's pegylated recombinant FVIII (rFVIII)
BU	Bethesda unit
(US) CFR	(US) Code of Federal Regulations
CHO	Chinese hamster ovary
CI	confidence interval
CL	total body clearance
Cmax	maximum plasma concentration
(e)CRF	(electronic) case report form
CTA	Clinical Trial Agreement
DI	dose intensification
DMC	data monitoring committee
EC	ethics committee
eCRF	electronic Case Report Form
ED	exposure day
EDC	Electronic Data Capture
ELISA	enzyme-linked immunoabsorbent assay
EMA	European Medicines Agency
EQ-5D	EuroQol-5 dimension
ETP	endogenous thrombin potential
FVIII	factor VIII
GCP	Good Clinical Practice
GEE	general estimating equation

Abbreviation	Definition
GLM	general linear model
h	hour(s)
HAV	hepatitis A virus
HBcAb	hepatitis B core antibody
HBsAb	hepatitis B surface antibody
HBsAg	hepatitis B surface antigen
HBV	hepatitis B virus
HCV	hepatitis C virus
HCV Ab	hepatitis C virus antibody
HDL	high density lipoprotein
HIV	human immunodeficiency virus
HJHS	hemophilia joint health score
HRQoL	health-related quality of life
IB	investigator's brochure
ICF	informed consent form
ICH	International Council for Harmonisation of Technical Requirements for Registration of Pharmaceuticals for Human Use
IgA	immunoglobulin A
IgE	immunoglobulin E
IgG	immunoglobulin G
IgM	immunoglobulin M
INR	international normalized ratio
IP	investigational product
IR	incremental recovery
ITI	immune tolerance induction
IU	international unit (s)
i.v.	intravenous(ly)
LDL	low density lipoprotein
MRI	magnetic resonance imaging
MRT	mean residence time

Abbreviation	Definition
NMC	non-medical complaint
PCR	polymerase chain reaction
PD	pharmacodynamic
pdFVIII	plasma-derived factor VIII
PEG	polyethylene glycol
PK	pharmacokinetic(s)
PP	per protocol
PRO	patient reported outcomes
PTP	previously treated patient
rFVIII	recombinant factor VIII
SAE	serious adverse event
SAER	serious adverse event report
SAS	Safety Analysis Set
SF-36	Short form-36 questionnaire
SIC	subject identification code
SUSAR	suspected unexpected serious adverse reaction
SWFI	sterile water for injection
T _{1/2}	plasma half-life
TGA	thrombin generation assay
T _{max}	time to maximum concentration in plasma
US	United States
VLDL	very low density lipoprotein
V _{ss}	volume of distribution at steady state
VWF	von Willebrand factor

